6.2 Secondary Endpoints

The secondary measures of effectiveness will include: a) change in pre-pilot and post-pilot questionnaire scores regarding CKD knowledge, self-efficacy, self-management, eHealth literacy and disease-related quality of life; b) change in baseline BP (as determined by the first BP measure transmitted) compared to mean BP after 4, 8, and 12 weeks, and c) change in mean step count in first week compared to mean step count after 4, 8, and 12 weeks.

An additional endpoint includes an assessment of “Reach”, which will be the number and characteristics of participants enrolled in the study.

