- 2) **Developing Goals and Action plan:** setting personalized goals for blood pressure self-monitoring and physical activity
 - Patients will complete a patient-generated “action plan” to assist in developing goals to help them initiate changes and achieve success in managing their condition effectively
 - Develop goals for blood pressure control by the end of the study and the level of adherence to blood pressure measurements
 - Develop daily step count goal for physical activity over the study period
- 3) **Support Adherence and Increase Self-efficacy:**
 - Provide personalized daily and weekly texts to encourage participation and progress towards blood pressure monitoring, physical activity goals
 - For blood pressure readings that are texted to the Way to Health platform, the participant will receive predefined comment on the control of their blood pressure
 - For each daily step count transmission, the participant will also receive similar feedback
 - Additionally, if the participant elects to enroll an accountability sponsor, progress will be shared with this individual
- 4) **Monitoring:**
 - For the participants using the OMRON Connect app, self-monitoring will be captured by electronically recording blood pressure measurements via Bluetooth by participant using a wireless blood pressure device (OMRON 5 series cuff)
 - CKD patients will be asked to self-measure blood pressure using a blood pressure cuff at home at least 3 times per week and then further personalized by goal-setting
 - Remote monitoring of physical activity will be done via a physical activity sensor (Fitbit Inspire 2) that is worn as a watch and link the data to the Fitbit app in order to help patients monitor their own personal progress.
- 5) **Social Support:** support through kin/sponsor
 - As indicated above in supporting adherence, by sharing feedback and progress with family members, peers or any other identified sponsor/support aims to support adherence.
 - In addition, there will be a link provided to the available social support:
 - Peers Lending Support- free, anonymous phone calls with other CKD patients (<http://www.kidney.org/patients/peers/index.cfm>)
 - Participants will also be provided with directions to access friends and a community with the FitBit App.
 -

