Participants will be asked to complete baseline questionnaires and report on their sociodemographic characteristics, including age, gender, highest level of education, and race/ethnicity, baseline step counts on their smartphone or on a computer. They will also be asked to fill out an action plan for their BP and daily step count goals. The intervention will commence after these baseline measures have been collected.

At the end of the study, qualitative interviews will be scheduled with willing participants to provide an in-depth understanding of the factors that may facilitate or diminish the acceptability of the intervention and adherence to the implementation. Open-ended inductive questions will be used to elicit user perspectives and experiences of the intervention, allowing participants to freely describe their experiences and views in their own way. Interviews will be audio-recorded, fully transcribed and analyzed thematically.

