6.1 Primary Endpoints

The RE-AIM framework, which focuses on five dimensions (reach, effectiveness, adoption, implementation and maintenance), considered to be important for behavioral health interventions will guide the evaluation for the primary endpoints of feasibility of the SMART-HABITS program.

- 1) Adoption: a) participant retention rate at 4, 8, and 12 weeks, b) Percentage of participants who used SMART-HABITS at any point during the 12 weeks.
- 2) Adherence: a) percentage of self-monitored BP transmissions performed out of the recommended and b) percentage of step count data transmissions out of the recommended.
- 3) Acceptability: a) improvement of the pre- and post-study scores on the attitudes toward mHealth questionnaire, b) satisfactory ratings on the ease of use survey during the study and at the end of the study and, c) interview feedback after the end of the pilot study.

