6.3 Statistical Methods

We will describe the study population with mean values (standard deviations) or medians and quartiles as appropriate for continuous variables and percentages for categorical variables using STATA software. Specifically, we will report the enrollment rate, the retention rate, and participant ratings on ease of use surveys. We will explore if these characteristics differ by age, gender, and education level with analysis of variance and Pearson's Chi2-testing. We will report the adoption as the percentage of participant still enrolled in the intervention at 4, 8, and 12 weeks and the percentage of participants who used SMART-HABITS at any point during the 12 weeks of the pilot trial. We will report the percentage of the self-monitored BP transmissions performed out of the recommended and also the percentage of the step count data transmissions out the recommended during the pilot trial.

We will perform an exploratory analysis of the change in 1) pre- and post-trial questionnaire scores, and 2) baseline BP and first week mean step count compared to the mean BP and step counts after 4, 8, and 12 weeks using paired t-tests, recognizing that over time the amount of information will diminish as we anticipate fall out, but also, a longer time for the intervention to have an effect. We will explore the association of baseline questionnaire scores with adoption and adherence with linear regression models adjusted for age, sex, race, and education. These will be exploratory analyses since the study was not powered to detect a statistically significant difference. We hypothesize that higher adherence and adoption will be associated with increased scores on baseline measures of self-efficacy, attitude toward mHealth, and self-management. We will also explore for trends in adherence with generalized linear mixed effects models and if blood pressure control or amount of steps modifies trend in adherence.

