7.1 Description

The intervention will utilize the Way to Health platform to provide: a) text message reminders, b) text message tailored feedback in response to transmitted data on blood pressure (in the text message arm) and daily step counts, c) positive affirmation text messages sent throughout the study to encourage behavior participation, d) provide links to educational resources, including a video on demonstrating how to correctly perform blood pressure self-mentoring in the portal, e) provide links to community resources and CKD patient forums within the portal, and the f) option to select a accountability partner to share the participant's reminders and feedback. The intervention was developed using a theory-based, and evidence-based approach.

Study Protocol: Supporting Self-Management of Healthy Behaviors (SMART-HABITS)

The Way to Health platform is an automated information technology platform that integrates wireless devices, clinical trial randomization and enrollment processes, messaging (text, e-mail, voice), self-administered surveys, and secure data capture for research purposes.^{141,142} Way to Health has been used in prior behavior intervention studies.¹⁴³⁻¹⁴⁶

At enrollment, a questionnaire (see Appendix IV) will be completed by all participants to capture demographics, kidney disease knowledge, ability to manage kidney disease, confidence in managing kidney disease, opinions of and ability to use mobile health technology. At enrollment, participants will complete a patient-generated “action plan” (questions in Appendix IV) in order to set realistic goals and encourage participants to create goals that involve positive action- with the minimum targets. Participants will develop short-term goals to help initiate changes and achieve success.

Participants will be asked to check their BP at least three times per week and then to communicate these BP readings with the research team using text message or with the OMRON Connect app (depending on the phase- please see below), and upon receipt, the participants will then receive tailored feedback.

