Participants will be asked to set a daily step goal of at least 3,000 steps per day at the start of the study and transmit their step count information to the research team on a daily basis. By providing a minimum threshold puts more emphasis on encouraging more sedentary individuals to walk more and less emphasis on getting highly active individuals to be more active. Participants will be reminded once a day in the evening to sync their steps with the FitBit app in order to transmit them to the Way to Health platform. Participants will receive daily individual performance feedback on their steps from the previous day. Participants will later be sent messages to see if they would like to increase their daily step goal.

Participants will be instructed how to correctly undertake BP self-monitoring to promote self-efficacy through a demonstration video available on Way to Health. Participants will be asked to rehearse self-monitoring at the initial study visit via a secure video-based platform using Zoom.

- Phase 1 (weeks 1-6):
 - After consenting to participate in the study, participants will be randomized to start with Texting (Arm 1) or the OMRON Connect App (Arm 2) to communicate BP readings.
 - Each arm will receive specific instructions pertinent to the specific phase tasks - available as a google document and will also be mailed at the beginning of the study (Appendix II).
 - Participants randomized to the texting arm in Phase 1 will receive automated text message reminders to check their BP on a personalized basis (minimum of three days per which) as participants will choose which days and times to receive these reminders at the beginning of the study. Participants will then transmit the BP readings with text message to the secure Way to Health server. If a blood pressure reading is not received within 3 hours, another reminder will be sent. Automated text message feedback will be sent after the BP reading is recorded with a tailored message regarding any further required actions based upon the BP readings obtained. Any participant with a single systolic blood pressure reading >200mmHg or two consecutive systolic blood pressure readings >180 mmHg or diastolic blood pressure readings >110 mmHg will be contacted immediately by an MD ([name]) for assessment (including evaluation for symptoms of hypertensive emergency) and referral to the emergency department, if indicated. Please see full text message algorithm (Appendix VII).

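### Baseline BP is a single first reading although at least three a week are requested; a 7-day-mean baseline reported beside it would modestly sharpen the exploratory BP-change estimate at no extra burden

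*Combined protocol and SAP*

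**What the plan says.** Section 6.2 lists as a secondary measure "change in baseline BP (as determined by the first BP measure transmitted) compared to mean BP after 4, 8, and 12 weeks". Baseline is thus one reading, while each later value is a mean. The next item in the same sentence compares later step counts with a mean over the first week. Section 6.3 keeps this asymmetry: "baseline BP and first week mean step count compared to the mean BP and step counts", analysed by paired t-tests at 4, 8 and 12 weeks and labelled exploratory.

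The readings for an averaged baseline are already requested. Section 1.2 asks patients to "self-measure blood pressure using a blood pressure cuff at home at least 3 times per week", and Section 7.1 repeats this: "Participants will be asked to check their BP at least three times per week".

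Section 5.2 calls the efficacy measures secondary or exploratory and says that the study is not powered for them. Section 3.3.1 limits enrolment to 40. No BP SD, correlation between readings or target interval width is given. The BP mean in Section 5.1 comes from historical records and serves eligibility only.

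**The concern.** One home reading is a noisy measure of a person's usual BP. The same reading is the comparator at 4, 8 and 12 weeks, so any error peculiar to it enters all three comparisons in full. Averaging the first week's readings would reduce that noise using data that participants are asked to send anyway, and the plan gives no reason for treating BP differently from steps.

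The stake is small. Whether BP control changes is one of the research questions in Section 2, but no decision rule uses the answer and no feasibility endpoint depends on it. What could be gained is a somewhat tighter estimate of BP change that leans less on one measurement.

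**Working it through.** The plan has no BP-change precision figure to reproduce, so the check is how much an averaged baseline would narrow the interval.

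**Inputs from the documents:** n = 40 (Section 3.3.1); one baseline reading, k = 1 (6.2); three requested readings a week, so k = 3 in a 7-day window at the requested minimum (1.2, 7.1); paired analysis (6.3).

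**Assumed inputs:** within-person SBP SD sw = 12 mmHg; SD of true change sd = 8 mmHg; correlation ρ = 0.3 to 0.5 between readings within each window; m = 3 or 12 readings in the later mean, because the plan does not define that window; two-sided 95% interval.

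**Formulas**

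Var(change) = sw²·{[1+(k−1)ρ]/k + [1+(m−1)ρ]/m} + sd²

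Half-width = t(0.975, 39) × √Var / √40 = 2.023 × √Var / 6.325

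**Example, ρ = 0.3, m = 12.** The later term is (1 + 11×0.3)/12 = 0.358.
- k = 1: 144×(1 + 0.358) + 64 = 259.6; half-width 5.15 mmHg.
- k = 3: the baseline term is (1 + 2×0.3)/3 = 0.533, so 144×(0.533 + 0.358) + 64 = 192.4; half-width 4.44 mmHg.
- Narrowing: 1 − √(192.4/259.6) = 13.9%.

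**Results.** The last column averages the variance over 50% of participants with three readings, 25% with two and 25% with one.

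| ρ | m | Half-width, k=1 (mmHg) | Half-width, k=3 (mmHg) | Narrowing, all send 3 | Narrowing, all send 2 | Narrowing, 50/25/25 |
|---|---|---|---|---|---|---|
| 0.3 | 12 | 5.15 | 4.44 | 13.9% | 10.2% | 9.3% |
| 0.3 | 3 | 5.40 | 4.72 | 12.6% | 9.3% | 8.5% |
| 0.5 | 12 | 5.41 | 4.93 | 8.8% | 6.5% | 5.9% |
| 0.5 | 3 | 5.58 | 5.12 | 8.2% | 6.1% | 5.6% |

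Full week-1 adherence therefore gives about 8–14% (roughly 0.5–0.7 mmHg), and the mixed case about 6–9%. With one week-1 reading the two baselines coincide and the gain is zero.

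**Sensitivity to the assumed SDs**
- Mixed case, ρ 0.3–0.5: sw/sd of 8/10 gives 3.6–5.7% and 15/5 gives 6.7–11.6%, so about 4–12%.
- All send three, sw 8–15 and sd 5–10: 8–17% at ρ = 0.3 and 5–11% at ρ = 0.5.
- Wider grids, all send three: with sd 8–15, sw 8–12 and ρ 0–0.7, about 2–25%. A model with within-period correlation 0.5–0.8 and baseline-to-follow-up correlation 0.3–0.6 gives about 5–26%.

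**Cost in absorbed change.** Averaging three readings lowers mean squared error only if the baseline absorbs less than √[sw²·(2/3)(1−ρ)/n] of the true change. At ρ = 0.3 this is √(144×0.467/40) = 1.30 mmHg; at ρ = 0.5 it is √(144×0.333/40) = 1.10 mmHg.

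Take readings on days 0, 2.33 and 4.67 (mean day 2.33). A change that builds linearly to completion at 28 days is absorbed by 2.33/28 = 8.3%, or 0.4 mmHg of an assumed 5. A change complete straight after the first reading is absorbed by two thirds, or 3.3 of 5 mmHg. The first is below break-even and the second is well above it, so neither baseline is better under all assumptions.

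**The case against.** The strongest defence is that the first reading is the one least exposed to the intervention. In the texting phase, "Automated text message feedback will be sent after the BP reading is recorded". Reminders go to both arms, and Section 7.1 also gives OMRON app users similar feedback, although the schema in Section 3 and the opening list of 7.1 mention tailored BP feedback only for the text arm. Section 4.1 starts the intervention once baseline measures are collected, so a 7-day mean lies largely inside it. This stands, and it is why the averaged baseline should not replace the planned one. It does not rule out showing the averaged baseline as a second analysis: the plan already accepts a first-week baseline for steps.

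The number of readings averaged also depends on engagement, and "percentage of self-monitored BP transmissions performed out of the recommended" is itself a primary adherence endpoint. Frequent senders could have more early change absorbed; those who send one reading have none absorbed. This stands too, and calls for reporting the counts.

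The step-count parallel is imperfect, since steps are transmitted daily and BP about three times a week. That weakens the argument from consistency but not the precision argument.

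Three stronger readings are tempting, and the documents support none of them:
- **That the baseline is wrong or biased.** It is defined in advance, and nothing shows an error in the first reading or its direction.
- **That a practice reading contaminates it.** Section 7.1 says "Participants will be asked to rehearse self-monitoring at the initial study visit via a secure video-based platform using Zoom" but not that any such reading is transmitted. At most this invites a clarifying sentence.
- **That the step baseline is inconsistent.** Section 4.1 also collects "baseline step counts on their smartphone or on a computer" without saying how they are used, but 6.2 and 6.3 agree on a first-week step baseline. That is a separate clarification.

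**Conclusion.** The point holds as a cheap, minor improvement to an exploratory outcome. The planned one-reading baseline is a defensible choice whose trade-off the plan does not discuss.

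For correlations below 1, a mean of two or more readings has lower variance than one reading, so the direction of the gain is secure when more than one week-1 reading is sent. Its size rests on assumed SDs and correlations. The 8–14% figure also needs every participant to send three week-1 readings, and adherence is what this trial sets out to learn. The 6–9% figure, or about 4–12% over the SD pairs tried, is the more cautious guide. The percentages do not depend on n. The half-widths and the break-even values do.

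**What to change.** In Sections 6.2 and 6.3:

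1. Keep the first-reading analysis as planned.
2. Pre-specify beside it the same paired analysis with baseline BP defined as the mean of all readings transmitted within 7 days of the first transmitted reading. Use whatever number is sent, without extending the window.
3. Report the number of readings behind each participant's baseline.
4. Keep the readings used for the 7-day baseline out of the later means. This requires stating the reading window for the 4-, 8- and 12-week means, which the plan leaves open.
5. Present the two estimates side by side and note that a difference between them may reflect early change absorbed by the 7-day mean or error in the single reading.

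The cost is a few sentences of analysis wording, ideally settled before BP data are examined. No extra visits, readings or participants are needed. The downside is the early change that the second baseline may absorb, to a degree that varies with adherence; reporting both estimates makes that visible.

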6.3 Statistical Methods

We will describe the study population with mean values (standard deviations) or medians and quartiles as appropriate for continuous variables and percentages for categorical variables using STATA software. Specifically, we will report the enrollment rate, the retention rate, and participant ratings on ease of use surveys. We will explore if these characteristics differ by age, gender, and education level with analysis of variance and Pearson's Chi2-testing. We will report the adoption as the percentage of participant still enrolled in the intervention at 4, 8, and 12 weeks and the percentage of participants who used SMART-HABITS at any point during the 12 weeks of the pilot trial. We will report the percentage of the self-monitored BP transmissions performed out of the recommended and also the percentage of the step count data transmissions out the recommended during the pilot trial.

We will perform an exploratory analysis of the change in 1) pre- and post-trial questionnaire scores, and 2) baseline BP and first week mean step count compared to the mean BP and step counts after 4, 8, and 12 weeks using paired t-tests, recognizing that over time the amount of information will diminish as we anticipate fall out, but also, a longer time for the intervention to have an effect. We will explore the association of baseline questionnaire scores with adoption and adherence with linear regression models adjusted for age, sex, race, and education. These will be exploratory analyses since the study was not powered to detect a statistically significant difference. We hypothesize that higher adherence and adoption will be associated with increased scores on baseline measures of self-efficacy, attitude toward mHealth, and self-management. We will also explore for trends in adherence with generalized linear mixed effects models and if blood pressure control or amount of steps modifies trend in adherence.

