- Arm 2 (first 6 weeks): push notification reminders via OMRON Connect app on participant's phone to check BP and BP readings shared via OMRON app
- Start of week 7: Arms cross-over
- All participants:
 - o Personal dashboard with access to educational and social support resources
 - o Daily text message reminders and feedback for step count data
 - o Re-engagement protocol for low participation
 - o Weekly feedback on BP monitoring adherence

Outcome assessments (end of 12 weeks)

- Primary outcome assessments of adoption, adherence, and acceptability
- Secondary outcome assessments of effectiveness and reach

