3.2 Allocation to Treatment Groups

Participants will be prospectively enrolled and randomized into one of two arms. Randomization will occur after enrollment on the Way to Health Platform utilizing random number generator. Specifically, permuted block randomization will be used for balance between cross-over arms throughout the investigation. The study coordinator will maintain the master list and securely store the randomization files.

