 - Participants randomized in Phase 1 to the OMRON Connect App arm will complete the same survey questions as those in the Texting Arm. Participants using the OMRON connect app will also receive reminder messages on a similar frequency as the texting arm and will also be customized the participant's schedule as they can choose which days and times to receive push notification reminders delivered by the OMRON connect app. Upon receipt of the BP reading, participants will receive similar BP feedback (Appendix VII).
- Phase 2 (weeks 7-12):
 - At the conclusion of week 6, individuals will “crossover” to the opposite study arm and will continue in the study for an additional 6 weeks using the opposite technology to communicate their BP readings.

Motivating and positive affirmation messages will be sent to participants on a weekly basis (Appendix VII). After 4 weeks,

Study Protocol: Supporting Self-Management of Healthy Behaviors (SMART-HABITS)

and 8 weeks of the intervention, a usability survey (Appendix V) will be sent out to assess the ease of use of SMART-HABITS. Automated messages will be sent at key milestones to promote adherence to study procedures. Weekly feedback will be sent the morning after the end of the week. Daily feedback on performance from the prior day will be sent each morning.

Within SMART-HABITS' smartphone web-based application, there will be a portal which provides:

- Educational information that incorporates both clinical and lay-experiential CKD knowledge: Educational resources will present the health-related benefits of self-monitoring, reducing blood pressure, and increasing physical activity. Positive expectations will be outlined by ways that use self-monitoring BP and increasing physical activity may reduce the chances of experiencing negative health consequences.
- Graphical displays of personally set goals and real-time progress to goals
- Web links to social support

Throughout the study, if participants are identified to have low engagement with the intervention, identified through remote monitoring and defined as no BP readings for >1 week or no step counts in 4 days, they will undergo a re-engagement protocol. The re-engagement protocol includes the research team contacting participants with text messages to re-engage them and if after two attempts, the participant continues to not be engaged, they will be called and interviewed over the phone to provide more granular information to assess real-time barriers.

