9.1 Treatment Assignment Methods

All participants in the study will be assigned to the interventions but in a different order (first 6 weeks or second 6 weeks of the study) since this is a cross-over design.

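### The order of BP-reporting mode is randomised with a cross-over at week 7, but Sections 6.1 to 6.3 plan BP-transmission adherence as one percentage and no planned analysis uses mode, period or sequence (free exploratory improvement)

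*Combined protocol and SAP*

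**What the plan says.** Section 3.2 states that "permuted block randomization will be used for balance between cross-over arms throughout the investigation". Section 7.1 identifies what is randomised: whether a participant starts with texting or with the OMRON Connect app to communicate BP readings. After week 6 each participant "will continue in the study for an additional 6 weeks using the opposite technology to communicate their BP readings". Section 9.1 confirms that everyone is "assigned to the interventions but in a different order (first 6 weeks or second 6 weeks of the study"). The prompts differ by mode as well. The schema in Section 3 gives Arm 1 text reminders and Arm 2 "push notification reminders via OMRON Connect app".

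The analysis sections do not take this structure up. Section 6.1 defines BP adherence as the "percentage of self-monitored BP transmissions performed out of the recommended". Section 6.3 repeats it for the pilot as a whole: "We will report the percentage of the self-monitored BP transmissions performed out of the recommended". The only model for adherence over time will "explore for trends in adherence with generalized linear mixed effects models and if blood pressure control or amount of steps modifies trend in adherence". The other adherence models in Section 6.3 regress on baseline questionnaire scores, adjusted for age, sex, race and education. Sections 6.1 to 6.3 nowhere mention mode, arm, phase, period or sequence.

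Section 2 asks whether patients will adhere to the programme's prompts. It does not ask whether one mode does better than the other. Sections 5.2, 6 and 6.4 say that the study is a feasibility pilot, not powered for efficacy, with no formal sample size.

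**The concern.** Order of mode is the only randomised factor, and no planned analysis uses it. One percentage over both modes averages away any difference between them. The trial therefore collects, in randomised order, information on which kind of prompt people respond to, but has no planned output that shows it. That information bears on the Section 2 question about adherence to prompts and on how the programme might be refined.

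There is a secondary effect on the trend model. The week-7 switch falls inside the 12 weeks being modelled, and mode is not among the terms named. If the two sequences end up unequal in size, part of a mode difference will appear as a rise or fall in average adherence over time.

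**Working it through.** The plan has no sample size, power or precision figure to reproduce. All rates and SDs below are assumptions.

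**Inputs from the documents.** At least 3 readings a week (Sections 1.2 and 7.1); two 6-week phases (Sections 3 and 7.1); N = 40 (Section 3.3.1); 20% loss as the trigger for enrolling more patients (Section 9.5), used here only to set n = 40 × 0.8 = 32. Equal allocation is assumed from the stated aim of balance; the ratio is not given.

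**1. What the single percentage can show.** Recommended readings at the minimum are 3 × 6 = 18 per participant per phase, 18 × 40 = 720 per mode and 1,440 in all.
- 80% by text, 60% by app: (0.80 × 720 + 0.60 × 720) / 1,440 = 70%.
- 70% in both: 70%.

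The planned figure is the same in both cases.

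**2. Effect on the trend, if it is fitted as linear in weeks 1 to 12** (the form is not stated). The least-squares slope of a unit step at week 7 is 18/143 = 0.126 per week. A 20-point mode difference gives 20 × 18/143 = 2.52 points a week, falling in text-first participants and rising in app-first participants.
- 20 and 20 remaining: the average effect is 0.
- 20 and 12 remaining (all of a 20% loss in one sequence, an extreme case): (20 − 12)/32 × 2.52 = 0.63 points a week, or 0.63 × 11 = 6.9 points from week 1 to week 12.

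**3. Why the mode comparison needs a period term.** Suppose adherence drops 10 points in phase 2 whatever the mode. The crude within-person text-minus-app difference is then off by 10 × (20 − 12)/32 = 2.5 points with 20 and 12 completers, and by 0 with 20 and 20.

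**4. Why that period term should not go into the trend model.** Over weeks 1 to 12 the correlation between a week-7 step and week is 18/√(143 × 3) = 0.87. Variance inflation is 1/(1 − 0.87²), about 4.1, so in an ordinary linear approximation the standard error of the trend about doubles (√4.1 ≈ 2.0). The coefficient also becomes a within-phase slope instead of the planned 12-week trend. Mode alone is uncorrelated with week when the sequences are equal. With 20 and 12 completers the correlation is 0.25 × 0.87 = 0.22, an inflation of 1/(1 − 0.22²) = 1.05.

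**5. Precision of the mode difference.** Half-width of the 95% CI = t(0.975, n − 2) × SD / √n, with equal sequences and SD that of the within-person difference in percentage points.

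| n | SD 20 | SD 30 |
|---|---|---|
| 40 | ±6.4 | ±9.6 |
| 32 | ±7.2 | ±10.8 |

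**The case against.** The strongest reply is that no stated aim is harmed. Section 2 asks about the programme, all participants receive both modes, and the plan disclaims powered inference. That stands, and it is why the point is an improvement and not an error.

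A reader might go further in several ways that the documents do not support.
- *That a mode difference would never be reported.* The plan only leaves it unplanned. Mode is known for each reading, so a later analysis remains possible, though it would be post hoc.
- *That the trend model is biased.* The average trend is affected only if the sequences become unequal. Permuted blocks aim at balance, and 20% loss is the level at which Section 9.5 would enroll more patients. The model's full list of terms is not given either, so the absence of mode is read from silence.
- *That the comparison was intended and forgotten.* Section 1.1 speaks of a single group and Section 3 of a cross-over, so Section 6 may predate the cross-over. This is conjecture.
- *That the open denominator undermines the comparison.* Section 1.2 has BP checks "at least 3 times per week and then further personalized by goal-setting", which leaves the level of adherence ambiguous. But goals are set at enrollment, and later increases are described only for steps. The ambiguity does not by itself bias a within-person comparison.
- *That binomial variation sets a lower limit on the half-width.* With independent readings, 70% adherence in both modes gives ±4.9 at n=40, but 90% gives ±3.2. The value depends on the assumed rate and is not a floor.

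It also stands that the contrast is between whole reporting packages. Section 7.1 describes a repeat reminder after 3 hours only for texting, and Section 1.2 has app readings captured by Bluetooth. The end-of-study interviews (5 to 10 participants, Section 9.5) may reveal a preference but give no adherence figure by mode.

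**Conclusion.** The point holds as a free exploratory improvement. The randomised factor enters no planned analysis, and the single adherence percentage cannot distinguish 80%/60% from 70%/70%. The feasibility endpoints remain reportable as written.

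The leak into the trend is conditional. It is zero with equal sequences, and 0.63 points a week in an extreme 20-to-12 split with an assumed 20-point mode difference and a linear trend. A mode difference could be estimated to within about ±6 to ±10 points at n=40, and ±7 to ±11 at n=32, if the SD of the within-person difference is 20 to 30 points. That is enough to describe a difference but does not support a claim of power.

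**What to change.** In Section 6.3, labelled exploratory and with no power claim:

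1. Report the percentage of recommended BP transmissions by mode and by 6-week phase, with the number of participants in each cell and the same stated denominator in both phases.
2. Fit a separate model for the mode comparison with mode, period and sequence as fixed effects and a participant random effect. Report the text-minus-app difference in percentage points (as a marginal difference if a logit link is used) with a 95% CI. In the planned 12-week trend model add mode only, not a period step.
3. State the limits. No washout is described, and sequence is aliased with carry-over. Participants who leave before week 7 contribute to one mode only. Precision rests on assumed SDs, and the contrast is between reporting packages, not message channels alone.
4. Before interpreting any difference, reconcile the descriptions of BP feedback by arm. The Section 3 schema and the opening list of Section 7.1 tie tailored BP feedback to the texting arm. Later text in Section 7.1 gives feedback after readings sent by either route and describes similar feedback for app users.

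Items 1 to 3 are wording only, with no added patients, visits or data. Item 4 is wording if feedback delivery is already settled. Appendix VII is not among the documents, so the sponsor must confirm this.
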